After children and parents complete assent and consent forms, they will be asked to complete all survey measures including demographics, household composition, physical activity and eating habits, screen use, puberty stage, overconcern with weight or shape, school grades, and psychosocial measures. Children and parents will be encouraged to complete online REDCap surveys on separate devices. The research coordinator will review all surveys for completeness before ending the call. Parents will be asked to schedule a second zoom call within the upcoming 3 weeks. An electronic cellular-connected scale (BodyTrace), a tape measure to measure height, and a food portion size booklet to use during the dietary recall will be mailed to participants. Parents will be emailed a lab requisition for their child to have fasting blood tests collected at their local Quest labs.

Measures in baseline appointment – part 2

During the second Zoom video appointment, child's and parent's heights and weights will be measured using the mailed tape measure and electronic scale, and children will complete a 24-hour dietary recall. Child weight measurements will be used to determine child's eligibility into the study (≥ 95 th BMI percentile for age and sex). After finalizing eligibility and completing all baseline measures, participants will be randomized.

Randomization:

Families will be randomized to treatment conditions after completing baseline measures, using Efron's biased coin randomization stratified by location, sex, and race/ethnicity, to promote balance on key characteristics that may influence weight changes, and allow examination of sex as a biological variable. Investigators and all data collection staff will

remain blinded to treatment condition assignment until all participants have completed the final follow-up assessments.

Interventions:

The research activities will be delivered as online videos and activities sent 9 times throughout the program. Parents will be emailed REDCap surveys that link to Qualtrics activities; one with a parent video/activity and one with a child video/activity. The WISE interventions encourage values affirmations and a growth mindset. The control videos and activities reinforce diet and physical activity messages that are part of the weight control program.

Follow-up Assessments

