4. PARTICIPANT POPULATION

a. Planned Enrollment

(i) We expect to enroll approximately 200 families. Because multiple eligible children and parents may be enrolled from a single family, this is expected to include up to 240 eligible children and 240 eligible parents.

(ii) We are the only site involved in this research. Therefore, the total sample will be approximately 200 families.

(iii) Children aged 10-16 years with obesity and their parents/guardians. Children and their parents are included because this is a study to test a family-based approach to reduce weight gain in children with obesity using online methods.

b. Age, Gender, and Ethnic Background

Based on past experience in the existing pediatric weight control treatments, we anticipate participants to be approximately: 55% girls, 45% boys, 50% white, 3% African-American, 25% Latino/Hispanic, 1% Native American, 8% Asian/Pacific Islander and 13% other (including multi-ethnic).

c. Vulnerable Populations

Up to approximately 240 10-16 year-old children with obesity (in 200 families).

Rationale for Involvement of Potentially Vulnerable Subjects.

Children with obesity are at increased risk of related morbidities, including hypertension, dyslipidemias, diabetes, non-alcoholic fatty liver disease, and atherosclerosis, among others, and future risk of heart disease, stroke and many cancers. However, most available pediatric obesity treatment programs produce only limited and non-sustained effects. There is a great need for new, innovative approaches to improve and sustain weight control among overweight and obese children. In the proposed trial, we will test the addition of several promising and potentially generalizable social psychological strategies.

To minimize risks and chance of harm, assent will be obtained from all children and consent will be obtained from parents/guardians for their child's and their own participation, after full explanation of the study, via zoom video call. Parents/guardians will be required to accompany their child during participation in the study zoom calls.

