Wise Social Psychological Interventions to Improve Outcomes of Behavioral Weight
Control in Children With Obesity

Statistical Analysis Plan

NCT04422951

May 13, 2022

Study Design: two-arm, parallel group, randomized controlled trial.

Primary Hypothesis: Compared to children randomized to receive a usual care behavioral pediatric weight management program alone, children randomized to receive a usual care behavioral pediatric weight management program plus the wise social psychological interventions will have a significantly attenuated BMI trajectory over 6 months.

Primary Outcome: Body mass index (BMI) trajectory over the 6-months duration of the study for each participant.

Primary Analysis, Statistical Model and Approach: We will use mixed effects linear regression techniques to address our aims. Such models are typically utilized in the clinical trials setting where repeated measurements are proposed.^{154,155} Specifically, we will regress BMI at a given time point on study arm, days since randomization, and an interaction between study arm and days since randomization. Also included in the model are a subject-specific random effect to account for the correlation of measurements over time within a subject and a group-specific random effect to account for the correlation among outcomes across subjects assigned to the same group and behavior coaches. Both random effects are assumed to be normally distributed. Finally, we include the randomization factors: sex and race/ethnicity. The proposed model can be expressed as:

$$\text{BMI}_{ij} = \beta_0 + \gamma_i + \delta_{j(i)} + \beta_1 \text{ treatment}_i + \beta_2 \text{ time}_{ijk} + \beta_3 \text{ treatment}_i \times \text{time}_{ijk} + \beta_4 \text{ sex}_i + \beta_5 \text{ ethnicity}_i + \varepsilon_{ijk},$$

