where ε_{ijk} is the random error term assumed to follow a normal distribution for the k^{th} observation corresponding to the i^{th} child assigned to the j^{th} group, γ_i is the subject-specific random intercept corresponding to the i^{th} child, and $\delta_{j(i)}$ is the group-specific random intercept corresponding to the j^{th} group in which the i^{th} child is nested. We are interested in drawing inference around β_3 that represents the difference in BMI trajectory over time between the two study arms. For this purpose, we will use a two-sided Wald test at the 0.05 level of significance. Our mixed effects regression approach most closely matches the study design and stratified randomization, and has advantages over a t-test endpoint analysis and other repeated measures analysis approaches for trial data including repeated measures ANOVA; it uses all available data, can accommodate differential lengths of follow-up, irregular measurement intervals, and missing data under reasonably flexible assumptions regarding the missing data mechanism.^{156,157}

Intent-to-Treat: We will adhere to intent-to-treat principles. All participants randomized will be included in the analysis and analyzed according to their original treatment assignment. While we expect limited loss to follow-up, our analysis allows subjects without complete data to be included in the analysis for their partially observed period. Such an analysis relies on a flexible assumption about missingness, namely that the data are missing related to observed features only (MAR). As a sensitivity analysis, we will also rely on multiple imputation-based methods that repeatedly impute values for those with incomplete data prior to fitting the mixed effects linear regression model. The imputation model can consider a large number of features (beyond those included in the primary analysis model). The sensitivity analysis will provide insight into the robustness of our findings to missingness and how missing data are handled.

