Detectable Difference, Sample Size, and Power: We will randomize a total of 160 participants (80 per study arm). We estimate sufficient power to address our aims. Estimates of power were performed using simulations (1000 simulations per scenario), which allowed us to consider a wide range of plausible assumptions and conditions, varying the sample size, retention rates, ICCs within individuals, ICCs within groups, BMI standard deviations, and combinations of trajectories of BMI decreases and increases and in the treatment and control groups. Across a wide range of assumptions and our planned total sample size of 160 children, or 80 children per study arm, we have at least 80% power to detect clinically meaningful differences in trajectories of 0.4 kg/m² or greater per 24 weeks. For example, a 0.6 BMI increase over 24 weeks in the control group and a 0.2 BMI increase over 24 weeks in the treatment group.

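### Families are randomised and siblings may enrol, but the primary Wald test of the treatment-by-time term ignores correlation between siblings' BMI changes

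*SAP*

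**What the plan says.** Protocol section 2a (Randomization) makes the family the unit of allocation: "Families will be randomized to treatment conditions after completing baseline measures". Section 4a plans about 200 families and allows more than one child from each: "Because multiple eligible children and parents may be enrolled from a single family, this is expected to include up to 240 eligible children". Siblings therefore always receive the same arm.

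The SAP (Primary Analysis, Statistical Model and Approach) regresses BMI on arm, time and their interaction. It includes "a subject-specific random effect to account for the correlation of measurements over time within a subject and a group-specific random effect", the second being for children who share a group and behavior coaches. Both are random intercepts. The subscripts denote child, group and observation; none denotes family. Inference is on β3, the arm-by-time interaction: "we will use a two-sided Wald test at the 0.05 level of significance".

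Under Intent-to-Treat, "All participants randomized will be included in the analysis and analyzed according to their original treatment assignment", and no rule selects one index child per family. The power section counts children, not families: "We will randomize a total of 160 participants (80 per study arm", half of 160 in each arm. Its simulations varied, among other inputs, "retention rates, ICCs within individuals, ICCs within groups, BMI standard deviations". No within-family correlation is listed.

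**The concern.** When families are allocated and several members are analysed, a valid standard error must allow for correlation within the family. Siblings share a household, a parent and the same arm's materials, so some correlation in how their BMI changes is plausible, and the SAP does not argue that it is zero.

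The existing random effects do not cover this. A difference in BMI level, whether it belongs to a child, a group or a family, drops out of within-child change. β3 is a contrast of changes, so its variance depends on how siblings' changes correlate. Even if the group term were read as family, a family random intercept would not help.

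With positive sibling correlation the primary test rejects too often under the null, the confidence interval is too narrow and the stated power is too high. With zero correlation, nothing is lost.

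**Working it through.** **The plan's own figure.** The SAP claims at least 80% power for 0.4 kg/m² per 24 weeks with 80 children per arm, but gives no SD, ICC or retention value, so the figure cannot be reproduced. Taking 80% as exact, the implied SD of 24-week change is 0.4 / (2.802 × √(2/80)) = 0.90 kg/m².

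**Inputs.** From the protocol: about 200 families and at most 240 children, taken here as 160 single children plus 40 pairs. From the SAP: 160 children and a two-sided 5% test. Assumed: the sibling ICC of observed BMI change (0.1, 0.3 and 0.6) and any number of pairs below the ceiling.

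**Closed form.** With m the number of children in a family:
- m₂ = Σm²/Σm
- design effect DE = 1 + (m₂ − 1) × ICC
- true error rate = 2 × [1 − Φ(1.96/√DE)]
- correct interval width relative to the naive one = √DE

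These error rates apply when differences in slope between children are otherwise handled and only family is ignored.

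| Pairs / children | m₂ | True error rate at ICC 0.1 / 0.3 / 0.6 | Correct interval wider by |
|---|---|---|---|
| 40 / 240 | (160+160)/240 = 1.333 | 5.4 / 6.2 / 7.4% | 1.7 / 4.9 / 9.5% |
| 20 / 220 | (180+80)/220 = 1.182 | 5.2 / 5.6 / 6.3% | 0.9 / 2.7 / 5.3% |
| 10 / 210 | (190+40)/210 = 1.095 | 5.1 / 5.3 / 5.7% | 0.5 / 1.4 / 2.8% |

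Example: 40 pairs at ICC 0.3 give DE = 1 + 0.333 × 0.3 = 1.10 and √DE = 1.049. Then 1.96/1.049 = 1.869, which gives 6.2%.

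**Simulation under the null.** 20,000 runs per setting (Monte Carlo SE 0.15 to 0.25 points); families randomised 1:1; visits at 0, 3 and 6 months; SD of change 0.90 and residual SD 0.4 (the latter assumed). The estimator is the within-child slope contrast, which equals the random-intercept estimate of β3 when data are complete. Rejection rates for 240 children with 40 pairs:

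| Standard error | ICC 0 | 0.1 | 0.3 | 0.6 |
|---|---|---|---|---|
| SAP model-based | 10.5% | 10.9% | 11.9% | 13.7% |
| Slope variation handled, family ignored | 5.2% | 5.6% | 6.5% | 7.5% |
| Clustered on family | 5.3% | 5.3% | 5.4% | 5.3% |

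The SAP's model is already at 10.5% with no sibling correlation, because it has no child random slope. That is a separate matter and is not counted here. By subtraction, family adds about 0.4 / 1.4 / 3.2 points; the first is close to Monte Carlo error. With 10 pairs the SAP rates are 10.5 / 10.3 / 10.9 / 11.5%, and the family-clustered rates are 5.0 to 5.3%. With 40 pairs and 15% of each follow-up visit missing, family clustering gives 5.2 to 5.3%.

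**Range of the ICC.** For visits at 0, ½ and 1 of follow-up, residual error contributes 0.4²/0.5 = 0.32 of the total change variance 0.90² ≈ 0.815, leaving 0.495 for true slopes. An observed ICC of 0.6 then needs a true-slope sibling ICC of 0.6 × 0.815/0.495 = 0.99, so 0.6 is an extreme. ICC 0.3 needs 0.49.

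**Power.** Scaling the ceiling share to 160 children gives about 133 families and 27 pairs: m₂ = (106+108)/160 = 1.337. The power ignoring family that is needed to keep 80% is Φ(2.802 × √DE − 1.96) = 81.3 / 83.6 / 86.7% at ICC 0.1 / 0.3 / 0.6. With 8 pairs (m₂ = 1.10) it is 80.4 / 81.1 / 82.2%.

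**The case against.** The strongest reply is about size. Neither the number of pairs nor the sibling ICC is in the documents, 240 children is a ceiling, and the sibling share among the SAP's 160 children cannot be derived. With 10 pairs and a low ICC the harm is undetectable. The effect also depends on how the variance of change splits. With residual SD 0.55, the ICC of observed change cannot exceed 0.26, since residual error takes 0.55²/0.5 = 0.605 of 0.815. With no slope variance, the simulation gives 5.3 to 5.4% for all three standard errors. The missing child slope is the larger problem, and family clustering would repair it too, so the whole gain should not be credited to siblings. Power loss is unproven, because the SAP claims at least 80%.

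All of this stands as a limit on magnitude. None of it shows that the written model accounts for siblings.

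Two further points are fair. A robust standard error corrects the variance only and leaves the model's covariance, on which its missing-at-random argument relies, unchanged; child and family random slopes are an alternative. And if children in different families share a group whose members change together, family clustering alone would not capture that. The protocol describes online activities sent to each family and mentions no such groups or coaches, so the SAP should say what the term means.

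**Conclusion.** The concern holds. The unit of randomisation is the family, siblings may enrol, and the primary test as written makes no allowance for siblings' BMI changes being correlated. Confidence in the omission and its direction is high: positive sibling correlation makes the test anti-conservative.

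The size is modest. With slope variation otherwise handled, the true error rate runs from 5.1% (10 pairs, ICC 0.1) to 6.2% (40 pairs, ICC 0.3), and reaches 7.4% only at an extreme ICC of 0.6. These figures rest on assumed ICCs and pair counts. The power claim may survive, but it was not tested against family clustering. This should be fixed because it affects the single primary test and the remedy is cheap; it does not by itself undermine the trial.

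**What to change.** Keep the model's point estimate of β3. State in the SAP that its two-sided Wald test and confidence interval use robust standard errors clustered on the randomised family, and that the multiple-imputation sensitivity analysis does the same. Rerun the power simulation with a stated share of sibling families and a stated within-family ICC of BMI change, and restate power if it falls below 80%. Separately, define what group means in the model; as a random intercept it has almost no effect on β3.

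The cost is one SAP sentence, a family identifier in the analysis data set and one rerun of the simulation. The price is slightly wider intervals and possibly a slightly lower stated power. Settling this before analysis also avoids a post hoc choice of standard error.

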2. STUDY PROCEDURES

a. Procedures

Recruitment and screening:

We intend to recruit 200 households of children ages 10 through 16 years with obesity who are enrolled in usual care pediatric weight management and their parents.

Pediatric weight management programs will be identified and asked to distribute a study recruitment flyer and/or email to their patients. All recruiting materials will direct potentially interested parents to our Stanford study website that describes the study and provides a REDCap screening survey to assess possible eligibility.

A copy of the approved consent and assent forms will also be available via a link on our Stanford study website.

To qualify, children must be enrolled in pediatric weight management and parents or legal guardians must complete an online eligibility screening questionnaire that is available on our study website in REDCap. At the start of the screening survey, they will read the waiver of documentation for recruitment and click continue to proceed to the screening questions. If a family meets preliminary eligibility criteria, they will be asked if they would like to schedule a baseline appointment (zoom video call). After they have scheduled an appointment, they will be emailed the consent and assent forms.

Baseline screening and measurement:

Parent(s) and child(ren) must attend an initial Zoom video call with a research coordinator. During this call and prior to collecting any data, we will explain all aspects of the study including data collection measures, intervention activities and randomization and obtain signed consent from the parent/guardian and signed assent from the child. All questions will be answered by study staff prior to families signing consent forms (parents/guardians) and assent forms(children). The consent/assent forms are on REDCap, which allows participants to use their mouse (desktop) or finger (mobile) to record signatures.

Measures in baseline appointment – part 1

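### Randomisation is stratified by location, sex and race/ethnicity, but the SAP names only sex and race/ethnicity as randomisation factors; a location main effect would correct the list but leave the tested slope unchanged

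*SAP*

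**What the plan says.** **Protocol, section 2a (Randomization)** describes "randomization stratified by location, sex, and race/ethnicity, to promote balance on key characteristics that may influence weight changes".

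**SAP, Primary Analysis, Statistical Model and Approach** states: "Finally, we include the randomization factors: sex and race/ethnicity". The equation agrees, with one coefficient for sex, one for ethnicity and none for location. The SAP also includes "a group-specific random effect to account for the correlation among outcomes across subjects assigned to the same group and behavior coaches". It defines that term as an intercept: it "is the group-specific random intercept corresponding to the" j-th group. The test is a two-sided Wald test of β3, the treatment-by-time coefficient. The same section says: "Our mixed effects regression approach most closely matches the study design and stratified randomization".

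**What location means** is not defined. Protocol section 4a says "We are the only site involved in this research", while section 2a says "Pediatric weight management programs will be identified and asked to distribute a study recruitment flyer and/or email to their patients" and section 4g admits families from anywhere in the continental USA. Groups and coaches appear in the SAP only. Of the study activities, the protocol says: "The research activities will be delivered as online videos and activities sent 9 times throughout the program".

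**The concern.** The SAP presents a list of the randomisation factors, and the list is one short. The protocol gives one reason for all three factors: they may affect weight change. If location does affect BMI change, the primary slope test makes no use of a factor the trial already randomises by.

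The gap also leaves a choice open at analysis. Location could be left out, added as a main effect, or taken to be the same as group. Because its levels are undefined, an analyst could not code it from the documents alone.

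The obvious remedy, adding location beside sex and race/ethnicity, needs checking, because the tested parameter is a slope and every listed covariate acts only on the level of BMI.

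**Working it through.** **1. The factor lists**

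| Factor | Randomisation (protocol 2a) | SAP main effect | SAP term on the slope |
|---|---|---|---|
| Location | yes | no | no |
| Sex | yes | yes | no |
| Race/ethnicity | yes | yes | no |

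The last column is empty for all three factors.

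**2. The SAP's power figure.** The SAP claims at least 80% power for 0.4 kg/m² per 24 weeks with 80 children per arm. This can be neither reproduced nor refuted, because no SD, ICC or retention value is given. Solving for the SD of 24-week change with complete data:

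SD = 0.4 / [(1.9600 + 0.8416) × √(2/80)] = 0.4 / (2.8016 × 0.1581) = 0.903

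The SE of β3 is then 0.903 × 0.1581 = 0.143. This SD is an implied value, used below only as a starting point.

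**3. Why a main effect does not move β3.** With three complete, equally spaced visits, a child's least-squares slope per 24 weeks is BMI at 6 months minus BMI at baseline. The β3 estimate is mean change in the treated arm minus mean change in the control arm. Any term that is constant over time within a child cancels. Fitted models confirm this:

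- Complete data (4 locations, intercept SD 5, residual SD 0.638, all assumed): β3 was identical to six decimals with and without a location main effect, and the mean SE was 0.14203 both times.
- About 20% dropout and irregular visit times: β3 changed by at most 0.006 kg/m² and its SE by at most 0.00004, on SEs of about 0.16 to 0.17.
- Child and group/coach random intercepts, 15% dropout, 3 or 8 locations, groups nested in, identical to or crossed with location: the SE changed by at most 0.011% and the estimate by at most 0.0045 kg/m².

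In the first two settings the SE of the level term β1 did fall, from 0.87–0.89 to 0.78–0.80. The main effect therefore works, but on a parameter that is not tested.

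**4. What a slope term could gain: hand check.** Let *s* be location's share of the variance in 24-week change. With three visits, the model estimates residual variance from two within-child contrasts, slope and curvature, with nearly equal degrees of freedom. Location inflates only the first. Without a location slope the estimated variance is therefore too large by v = ½[1/(1−s) + 1], and the SE by r = √v.

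- s = 10%: v = 1.0556, r = 1.0274
- s = 20%: v = 1.125, r = 1.0607

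Start from 80% power for the SAP test. If its SE is right on average, power with a location slope is Φ(2.8016r − 1.9600). At 10% this is Φ(0.918) = 82.1%, and at 20% Φ(1.012) = 84.4%.

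If randomisation balances locations perfectly, it is Φ(1.9600r + 0.8416 − 1.9600). At 10% this is Φ(0.895) = 81.5%, and at 20% Φ(0.961) = 83.2%.

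The gain is thus about 1.5 to 2.1 points at 10% and 3.2 to 4.4 points at 20%.

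**5. Simulation.** Setting: 160 children, effect 0.4 kg/m², three complete visits, an assumed 2/3 biased coin within location × sex × race/ethnicity, and the race/ethnicity and sex mix of protocol section 4b. There were 6,000 runs per cell, with the SD of change set in each cell (0.893 to 0.966) so that the SAP-type test has 80.0% power. Entries are changes in power, in percentage points.

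| Location share of variance in change | Random slope, 2–20 locations | Fixed location × time, 2–5 | Fixed, 10 | Fixed, 20 |
|---|---|---|---|---|
| 0% | −0.1 to +0.2 | −0.6 to −0.1 | −1.5 to −1.2 | −4.2 to −4.0 |
| 5% | +0.25 to +1.1 | +0.5 to +1.1 | −0.7 to 0.0 | −2.8 to −2.7 |
| 10% | +0.7 to +2.1 | +1.4 to +2.1 | +0.5 to +0.6 | −1.7 to −1.0 |
| 20% | +2.6 to +4.3 | +3.9 to +4.4 | +2.4 to +3.1 | +1.2 to +1.7 |

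The Monte Carlo SE of these differences is 0.06 to 0.43.

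**6. Type I error in the same runs.** SAP-type test 4.8–5.8%, fixed location × time 4.5–5.8%, random slope 4.6–5.8% (Monte Carlo SE about 0.28).

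**The case against.** **Sex and race/ethnicity do not help the slope test either.** This is correct. A reader might infer that two of the three factors sharpen the primary test and location alone is left out. The documents do not support that: all the listed covariates are main effects, and none bears on β3.

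**Why put location on the slope and not the other two?** The protocol gives one rationale for all three, so nothing in the documents ranks them. The reason is practical. Location's term has to be written anyway, and a random slope costs almost nothing. That makes the slope term a small efficiency gain added to a consistency correction.

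**The group/coach effect may already carry location.** It may. Children attend usual-care programs, and groups and coaches could belong to those programs; online delivery of the study activities does not rule this out. The documents do not settle the question, so the SAP should answer it. Even if group and location coincide, the term is an intercept and does not act on the slope.

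**The SAP's statement about matching the design is only a comparison** with a t-test and repeated-measures ANOVA. That is a fair reading, and the point does not depend on it. The factor list is short either way.

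**The reassurance on type I error is narrow.** It is. It covers the omission of location only. Nothing is said here about children's slopes varying individually or about siblings from one family.

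**Conclusion.** The concern holds as a minor point: a consistency correction with a small efficiency gain. The mismatch between the two factor lists is plain on the page.

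Three stronger readings are tempting and not supported:

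- *The primary test is invalid because a stratification factor is missing.* In the simulations, omitting location left type I error near 5%.
- *The trial falls short of its stated power.* The SAP-type test was set to 80% by construction. The loss is only relative to a model with location on the slope.
- *Adding location as a covariate repairs the test.* It repairs the list only.

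The possible gain is roughly 0 points at a 0% share, 1 to 2 at 10% and 3 to 4 at 20%. The number of locations and location's share of the variance in change are assumptions, since the documents give neither. The main simulation also assumes complete visits. That a main effect leaves β3 essentially unchanged does not depend on the assumed share.

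**What to change.** Before unblinding, amend the SAP's primary analysis section to:

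1. List location, sex and race/ethnicity as the randomisation factors.
2. State location's levels exactly as coded in the randomisation system.
3. State whether location is the same as, nested in or crossed with the group/coach effect.
4. Add one term that lets location act on the slope. Use a location random slope for time, dropped if it does not converge or its variance is estimated at zero. Fixed location × time may replace it only if the coded levels number 5 or fewer, with that count taken from the randomisation system before unblinding. Keep the group/coach intercept and add a location intercept unless the two coincide. In the fitted models the extra intercept changed the SE of β3 by at most 0.044%.

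Sex × time and race/ethnicity × time, with small categories pooled, can be a sensitivity analysis.

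**Cost.** Items 1 to 3 are wording. Item 4 changes the primary model but needs no new data, because location is already recorded for randomisation. If location has no effect, the random slope costs at most about 0.1 points, and the fixed form about 0.6 points with 5 or fewer levels. The fallback must be written down: with no location effect, the slope variance was estimated at zero in 55 to 69% of simulated trials, and the test then equals the SAP's own.

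### The SAP's covariates enter as level terms only and so barely touch the tested slope; pre-specifying sex, baseline age and puberty stage by time is a cheap change with a small, uncertain gain

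*SAP*

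**What the plan says.** The SAP (Primary Analysis, Statistical Model and Approach) regresses BMI on arm, days since randomization and their product, with random intercepts for child and for group. It then adds: "Finally, we include the randomization factors: sex and race/ethnicity". In the model formula these are the β4 and β5 terms, and neither is multiplied by time. Inference is on β3 alone, by a "two-sided Wald test at the 0.05 level of significance". The SAP also states: "Our mixed effects regression approach most closely matches the study design and stratified randomization".

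The protocol (section 2.a, Randomization) stratifies by location, sex and race/ethnicity, giving as one reason that these may affect change in weight. Section 2.a (baseline appointment, part 1) lists among the baseline measures "screen use, puberty stage, overconcern with weight or shape". Age is known for every child, because eligibility is age 10 to 16 with a BMI percentile for age and sex (section 4.g). Neither age nor puberty stage is a stratification factor or a term in the primary model.

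**The concern.** A child-specific intercept absorbs differences between children that are constant over time. Sex and race/ethnicity as level terms describe just such differences, whereas β3 is estimated from change within children. The stated adjustment then does no work on the one effect that is tested, although the protocol chose the stratification factors partly for their link with change in weight.

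Raw BMI is also expected to move with growth between ages 10 and 16. If age, puberty stage and sex predict 6-month change, that predictable part stays in the error of β3, and a chance difference between arms in age or puberty goes uncorrected. They may predict dropout as well, in which case including them would make the missing-at-random assumption easier to defend. At stake are some precision and protection against chance imbalance, not the validity of the trial.

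**Working it through.** **Inputs from the SAP.** Two-sided 0.05; 160 children, 80 per arm; and "we have at least 80% power to detect clinically meaningful differences in trajectories of 0.4 kg/m² or greater per 24 weeks". The power simulations varied "ICCs within individuals, ICCs within groups, BMI standard deviations", but no values are printed. On dropout the SAP says only "While we expect limited loss to follow-up". The documents give no R², so a range is assumed.

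**1. The plan's own figure.** The 80% cannot be reproduced without those values, but it can be back-solved. For 80% power, δ/SE = 1.9600 + 0.8416 = 2.8016, so SE(β3) = 0.4/2.8016 = 0.143 kg/m². With 80 per arm and no loss, the implied SD of 24-week change is 0.143/√(2/80) = 0.903 kg/m².

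**2. Do level terms affect β3?** With complete data at common times, arm-by-time varies only within children around each child's mean, while level terms vary only between children. The two are orthogonal, so the effect is exactly zero. To see what happens otherwise, the random-intercept model was simulated without the group effect: 160 children, three visits with jittered timing, 1,500 trials per setting. Assumed slope SD 0.80 and error SD 0.30 give a change SD of √(0.80² + 2 × 0.30²) = 0.906.
- No dropout, jittered visits: adding sex and ethnicity moved β3 by at most 0.0002.
- 10% dropout: by at most 0.003, with the SD of β3 unchanged to within 0.0001.
- Adding age and puberty as level terms also left the SD unchanged to within 0.0001.

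**3. Cost and gain of covariate-by-time terms.** Treating the test as a correctly calibrated comparison of change, p added terms multiply the variance by (1 − R²) × (N − 3)/(N − p − 3). With N = 160 and p = 3 the cost factor is 157/154 = 1.0195, or 1.0097 in SE. Break-even is R² = 3/157 = 1.9%. Power = Φ[2.8016/√(variance factor) − 1.9600].

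| Assumed R² | Variance factor | Power, p = 3 | Power with no charge for the terms |
|---|---|---|---|
| 1% | 1.0093 | 79.6% | 80.4% |
| 2% | 0.9991 | 80.0% | 80.8% |
| 5% | 0.9685 | 81.2% | 82.0% |
| 10% | 0.9175 | 83.3% | 84.0% |
| 20% | 0.8156 | 87.3% | 88.0% |

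If puberty were coded in categories so that p = 6, the cost factor is 157/151 = 1.040, break-even is 6/157 = 3.8%, and power at 1%, 2%, 5% and 10% is 78.9%, 79.3%, 80.5% and 82.5%.

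**4. Check by simulation of the repeated-measures model.** Here R² is the share of true slope variance. Multiplying by 0.64/0.82 = 0.78 converts it to a share of change variance. The SDs shown are from the runs with a true difference of 0.4 and 10% dropout.

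| Slope R² | Change R² | SD of β3, SAP model | SD with three by-time terms | Ratio | Ratio by formula |
|---|---|---|---|---|---|
| 0 | 0 | 0.1508 | 0.1521 | 1.009 | 1.010 |
| 5% | 3.9% | 0.1505 | 0.1513 | 1.005 | 0.990 |
| 10% | 7.8% | 0.1472 | 0.1438 | 0.977 | 0.969 |
| 20% | 15.6% | 0.1492 | 0.1379 | 0.924 | 0.928 |

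At 5% the null runs went the other way (0.1474 to 0.1458), so there is no clear change there. β3 was essentially unbiased throughout.

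**5. Chance imbalance.** A one-SD chance imbalance in the covariate score shifts the unadjusted β3 by √R² × 0.143. That is 0.032 at R² = 5% and 0.045 at 10%. A two-SD imbalance gives 0.064 to 0.090, or 16% to 23% of the 0.4 target.

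**The case against.** Randomization already protects β3 from bias, and the 5% error rate already allows for chance imbalance in unadjusted covariates. The SAP does not say that sex and race/ethnicity sharpen the slope; it says only that its approach reflects the design. The planned multiple-imputation sensitivity analysis may use features beyond the primary model, so age and puberty could inform the handling of missing data there. All of this stands. It makes the point an improvement rather than a defect. It does not make the level terms act on β3, and the imputation is only a sensitivity analysis that names neither variable.

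A reader might infer three stronger things that the documents do not support:
- **That the added terms are a free precision gain.** They cost about 1% in SE, lose slightly below R² of about 2%, and their benefit rests on an R² that no document states. The last column of the power table omits that cost and should not be relied on.
- **That level terms do strictly nothing.** This is exact only with complete data at common times. The SAP uses actual days since randomization and expects some loss, so the effect is negligible rather than zero.
- **That the change repairs the primary test.** With the assumed variation in slopes and only a random intercept, a true null was rejected about 12% to 13.5% of the time with or without the added terms. The missing random slope is a separate matter, and the power figures above presume a correctly calibrated test.

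**Conclusion.** The point holds as a low-cost improvement. The adjustment for sex and race/ethnicity does not act on the primary test in any way that matters, and two plausible predictors of BMI change that are available at baseline are left out. Crossing sex, age and puberty stage with time would change power from 80% to somewhere between 79.6% and 87.3% for assumed R² of 1% to 20%. The worst case, R² of zero, is about a 1% larger SE. Correction of chance imbalance comes with it. These figures rest on the SAP's 80 per arm and 80% power, on three added terms, and on an R² that has to be assumed. The effect of the level terms was checked under one assumed set of SDs, with dropout of 0% and 10%.

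**What to change.** Before unblinding, amend the SAP's primary model to include sex, baseline age and baseline puberty stage, each as a level term and as a product with days since randomization, the time scale the SAP already uses. Specify that:
- puberty stage enters as one ordered score, with a rule for missing values;
- only baseline values are used, because most baseline measures are repeated at 3 and 6 months and later puberty values are post-randomization;
- race/ethnicity stays a level term unless its sparse categories are collapsed first (the protocol, section 4.b, expects 3% and 1% in the two smallest).

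The cost is SAP wording, three slope terms with their level terms, and about 1% in SE if the variables turn out not to predict change. No new data, visits or children are needed. The random slope needs its own decision.
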